7.9 Recruitment

Eligible patients with PPDM from the outpatient clinic are contacted during scheduled clinical visits in the outpatient clinic. Information regarding medical history and previous treatment can be passed on from the treatment-responsible physician from medical records to study personnel. Potentially eligible patients from the outpatient clinic, may subsequently be contacted by study personnel, but only if permission has been granted by the treatment-responsible physician. This will be conducted in accordance with “Sundhedsloven § 46, stk 1”, under the responsibility of the primary investigator. Patients can be included, four weeks after discharge from an acute on chronic pancreatitis attack if they are clinically stable at the time of inclusion. We expect to enrol about 1 to 2 patients per week for sub study 1 and 5-10 patients per week for sub study 3.

7.10 Information about the study

All patients will be informed both oral and written before they decide whether they want to participate in the study. Furthermore, they will be informed that they can withdraw from the study at any given time without giving a reason. The participants are also allowed to have an assessor with them to the interview. Competent delegated personnel (medical doctors affiliated with the study or trained site staff) will give the oral information according to the Research Ethics Committee’s guidelines. The information interview will take place in quiet surroundings at one of our respective inclusion sites. During the interview, the participant will be informed thoroughly about the purpose of the study, the specific procedures the study entails, and potential benefits and risks. Any questions the participant have, will also be answered here. The written information (“Deltagerinformation”) is given or sent (in the case they contact us first) to the participants so they have it at least one day before the oral information takes place. After the interview where the participant has received information (oral and written) about the study, they are encouraged to go home and consider whether they want to participate in the study or not, for a minimum period of 24 hours. They may also sign the informed consent immediately if they are ready. After the participant has signed the informed consent and is included in the study, they will be receiving an ID-number. For additional information on informed consent and confidentiality see section 9.3.

8. Methods II: Data collection, management, and analysis

8.1. Data collection methods

8.1.1 Continues glucose and activity monitoring

Participants in sub study 1 will be provided with a CGM and an activity tracker. The CGM device consists of three components: A sensor, a transmitter, and a receiver. The receiver can be a mobile phone app or a dedicated device. The sensor penetrates the skin and is localized in the subcutaneous tissue on the upper arm or the abdomen and measures the interstitial glucose levels continuously. The signal is processed by the receiver and an interstitial glucose value is shown every 5 minutes. The participants will be trained in using the provided technologies at study initiation and use the devices continuously at home to measure and log tissue glucose levels, activity, and sleep for the entire study duration. Participants are in periods blinded to the results from both CGM and are informed that they remain responsible for monitoring and managing their blood glucose levels according to their usual standard of care, despite the telemonitoring. For technical challenges, participants can contact Steno Diabetes Centre by phone via a technical support line. Use of the devices do not restrict the daily activities of the participants.

8.1.2 Food diary and monitoring of insulin administration

Participants in sub study 1 are instructed to register their daily food intake and insulin administration (both basal and bolus) in a “food and insulin diary” during the CGM monitoring period. A diary provided by Diabetesforeningen is used. Thorough instructions on how to use and fill in the diary is provided by study staff. An example of the “food and insulin diary” is provided in the appendix.

8.1.3 Questionnaires

All questionnaires will be filled in by participants in sub studies 1 and 3.

8.1.3.1 *Clarke hypoglycaemia awareness survey*

The Clarke questionnaire for assessment of hypoglycemia awareness comprises eight questions characterizing the participant's exposure to episodes of moderate and severe hypoglycemia. It also examines the glycemic threshold for, and symptomatic responses to, hypoglycemia. A score of four or more implies impaired awareness of hypoglycemia.

8.1.3.2 *The Comprehensive Pain Assessment Tool Short Form (COMPAT-SF)*

The Comprehensive Pain Assessment Tool Short Form is a questionnaire that has been specifically developed and validated for pain assessment in patients with chronic pancreatitis. It comprises of 6 questions describing 5 pain dimensions: a) pain severity, b) pain pattern, c) factors provoking pain, d) widespread pain, and e) a qualitative pain-describing dimension. The questionnaire can be summarized in a total score in addition to the 5 pain dimension sub scores²⁴.

8.1.3.3 *Strength, assistance with walking, rising from a chair, climbing stairs, and falls (SARC-F) questionnaire*

The SARC-F questionnaire is a screening tool that can be rapidly implemented by clinicians to identify probable sarcopenic patients. The questionnaire screens patients for self-reported signs suggestive of sarcopenia, which include deficiencies in strength, walking, rising from a chair, climbing stairs, and experiencing falls. Each of the self-reported parameters receives a minimum and maximum score of 0 and 2, respectively, with the greatest maximum SARC-F score being 10²⁵.

8.1.3.4 EORTC QLQ-C30 questionnaire

The EORTC QLQ-C30 questionnaire is used to document life quality, physical function, and a number of other health-related parameters²⁶ and will be filled in by participants in sub study 1 at baseline. The questionnaire has been validated for assessment of quality of life in patients with chronic pancreatitis and is composed of single-item measures and multi-item scales with scores ranging from 0 to 100 after linear transformation of the raw score²⁷. A high score for a functional scale represents a high level of functioning, as does a high score for the global health status, while a high score for the symptom items represents a high level of symptomatology.

8.1.4 Biochemistry

Patients in sub studies 1 and 3 will have their pancreatic exocrine function evaluated by means of faecal-elastase test at baseline. At the same time, they will have routine clinical blood sample tests performed (including HbA1C, electrolytes, creatinine, albumin, haemoglobin, liver tests, pancreas specific amylase, c-peptide and autoantibodies) corresponding to approximately 20 ml blood. The blood samples are analysed immediately as part of routine clinical practice. Patients in sub study 1 will also have extra blood tests drawn to detect circulating levels of pancreatic hormones (insulin, glucagon, pancreatic polypeptide) and intestinal hormones (GLP-1 and GIP) as well as markers of hypoglycaemia and postprandial glucose excursions corresponding to approximately 30 ml blood. These blood samples will be separated by centrifugation and processed as plasma, serum, buffy coat, and full blood and subsequently transferred in aliquots to vials labelled with the protocol number (PPDM-CGM_2022), subject number, and date of sample collection. Samples will be frozen and stored at approximately -80°C or cooler in a freezer at Aalborg University Hospital until analysis. The samples will be batch analysed at a central laboratory to measure the analytes of interest. After the analyses, spare blood will be kept in the biobank for future research purposes and destroyed at the latest 15 years after termination of the study. Ethics according to “databeskyttelsesforordningen” and “databeskyttelsesloven” will be ensured in this regard. Based on the blood samples drawn at baseline (20 ml + 30 ml blood) a total of 50 ml blood will be drawn from each participant in sub study 1 and 20 ml from each participant in sub study 3.

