7.3 Eligibility criteria

7.3.1 Inclusion criteria PPDM patients

- Signed informed consent before any study specific procedures*
- Able to read and understand Danish
- Male or female age $\geq 18 \leq 80$ years
- A definitive diagnosis of chronic pancreatitis based on the M-ANNHEIM criteria²⁰
- A diagnosis of insulin treated PPDM based on the World Health Organization criteria for diabetes (HbA1c $\geq 6.5\%$ (48 mmol/mol) and/or fasting plasma glucose ≥ 126 mg/dl (7.0 mmol/l) > 3 months after diagnosis of pancreatitis

*a signed informed consent is waived for patients in sub study 2 which is a register-based study based on data from Diabetesdatabasen in the North Denmark Region.

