7.5 Concomitant medication and care

Along with participation in the studies included patients will continue their usual treatments and scheduled visits and examinations in the outpatient clinic according to usual standard of care and clinical guidelines.

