7.6.3 Explorative endpoints

In sub study 1 an arginine test is employed to study pancreatic endocrine secretory capacity (insulin and glucagon). In addition, various baseline characteristics of PPDM patients including pancreatic and intestinal hormone profiles are associated with CGM metrics to explore putative mediators of short-term glucose variability.

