Participants will undergo a total of 7 study visits, as illustrated in figure 2. The duration of the baseline visit (visit 1) is approximately 120 minutes, and the subsequent visits 15-30 minutes, making the total time required for participation in the study a maximum of 300 minutes. At the baseline visit, height and weight are registered, and body mass index is calculated. Pancreatic function (exocrine and endocrine) will be evaluated based on review of patients' medical records and supplemented by routine biochemical tests including autoantibodies and HbA1c. Also, blood is drawn for biobanking and assessment of basal intestinal and pancreatic hormone levels. An arginine stimulation test is done to assess endocrine pancreatic secretory capacity. Patients are instructed in use of an insulin and food diary and fill in questionnaires. Finally, the CGM sensor is mounted and activated. Every 10 days the CGM glucose sensor is changed by the participant at home based on instructions from study staff (or alternatively they can choose to have the censor changed in the diabetes outpatient clinic). After 20 ± 2 days (visit 2), participants meet to either unmask or remove the CGM. Then, on day 50 ± 2 (visit 3), the participant with unmasked CGM returns to unload the CGM transmitter, while the participants randomized to SMBG come in and the CGM is again mounted and masked. The study periods end at day 70 ± 2 , where participants meet for a follow-up visit (visit 4), where the CGM transmitter is unloaded. The food and insulin diary is collected and reviewed together with the patient to ensure accurate registrations of insulin administration and food intake. Patients fill in questionnaires and adverse events in relation to CGM monitoring or other study activities are registered. Since crossover will occur immediately at the end of the first study period, visit 4 in period 1 and visit 1 in period 2 are merged. Also, baseline data is only collected at the very first visit. In **Table 1** an overview of the various study activities in sub study 1 is reported.

Table 1: Participant timeline and study activities for sub study 1

	Study period 1			Study period 2			
	Baseline Visit 1 Day 0	Visit 2 Day 20	Visit 3 Day 50	Visit 4/1 Day 70/0	Visit 2 Day 20	Visit 3 Day 50	Visit 4 Day 70
Anthropometrics	X						
Biochemistry							
- Faecal elastase	X						
- HbA1c	X			X			
- Routine biochemistry	X						
- Blood for biobanking	X						
- Autoantibodies	X						
- C-peptide	X						

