8.1.5 Arginine stimulation test

An intravenous catheter is inserted into the cubital vein for blood sampling and arginine infusion with arterialization of the venous blood using the heated hand technique. At time -1 min 5 g argininehydrochlorid (100 mg/mL) is infused over 1 minute. Blood samples are drawn at time -15, 0, 2, 5, 10, 15 and 30 min for the analysis of blood glucose, plasma C-peptide and glucagon. These blood samples will be kept on ice and immediately separated by centrifugation and processed as plasma and subsequently transferred in aliquots to vials labelled with the protocol number (PPDM-CGM_2022), subject number, and date of sample collection. Samples will be frozen and stored at approximately -80°C or cooler in a freezer at Aalborg University Hospital until analysis. The samples will be batch analysed at a central laboratory to measure the analytes of interest. After the analyses, spare blood will be kept in the biobank for future research purposes and destroyed at the latest 15 years after termination of the study. Ethics according to “databeskyttelsesforordningen” and “databeskyttelsesloven” will be ensured in this regard. In total, 56 ml blood will be drawn from each participant during the arginine stimulation test.

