8.3 Plan for statistical analyses

8.3.1 Statistical methods

- **Sub study 1:** CGM metrics collected in periods with monitoring using CGM vs. SMBG are compared using multiple linear regression models. Further, regression models are fitted to investigate associations between baseline characteristics and measures of glucose variability.
- **Sub study 2:** HbA1c variability metrics are compared between PPDM and type 2 diabetes patients using multiple linear regression models. Hb1Ac level trajectories are visually characterized and latent class analysis is used to define distinct patient clusters.
- **Sub study 3:** Prevalence estimates of hypoglycaemia are reported as point prevalence estimates with 95% confidence intervals. Logistic and Poisson regression models are fitted to investigate associations between patient characteristics and hypoglycaemia risk.

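### Baseline circulating insulin is treated as a pancreatic hormone in patients who all inject insulin, so its exploratory link to CGM metrics is confounded by treatment

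*Protocol*

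**What the plan says.** - **Who is sampled.** Section 7.3.1 requires "A diagnosis of insulin treated PPDM based on the World Health Organization criteria for diabetes". Section 7.5 adds that "included patients will continue their usual treatments and scheduled visits and examinations in the outpatient clinic". The type 2 diabetes comparators give no biological material (7.3.3), so the hormone analysis concerns PPDM patients only.
- **What is measured.** Section 8.1.4 plans, for sub study 1, "extra blood tests drawn to detect circulating levels of pancreatic hormones (insulin, glucagon, pancreatic polypeptide"). Section 7.7.1 places this at the first visit, where "blood is drawn for biobanking and assessment of basal intestinal and pancreatic hormone levels". Neither section gives a fasting state, an interval since the last insulin dose, or the insulin assay.
- **What it is used for.** Under 7.6.3, baseline characteristics including "pancreatic and intestinal hormone profiles are associated with CGM metrics to explore putative mediators of short-term glucose variability". Section 8.3.1 says that "regression models are fitted to investigate associations between baseline characteristics and measures of glucose variability".
- **What else is measured.** C-peptide is in the routine baseline panel (8.1.4 and Table 1). The arginine test samples are taken "for the analysis of blood glucose, plasma C-peptide and glucagon" (8.1.5).

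**The concern.** In someone who injects insulin, the circulating concentration combines what the pancreas releases with what was injected. The split depends on the insulin product, the time since the dose and how far the assay reads insulin analogues. The protocol states none of these, so the value cannot be assigned to the pancreas.

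The trouble comes from how the value is used. Injected insulin is a direct cause of low glucose and of glucose swings. It therefore feeds both the supposed mediator (measured insulin) and the outcome (CGM metrics). An association could be reported as a pancreatic mechanism of unstable glucose when it only tracks dose size or timing. The direction might mislead too, if patients with least residual secretion inject most and so show higher values, but the documents do not allow that to be verified.

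At stake is the interpretation of one exploratory analysis, not the trial's main result.

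**Working it through.** The protocol states no figure on this point, so there is nothing to reproduce. The check is a reading of sections together, followed by an illustration.

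**1. Can the insulin value be attributed to the pancreas?** All sampled patients inject insulin (7.3.1), and usual treatment continues (7.5). The draw is called basal (7.7.1), but no time since the last dose is specified. The value is thus a mix of unknown proportion.

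**2. Could the recorded data separate the sources later?** Section 8.1.6 records regimen and daily units, which allows adjustment for usual dose. The diary (8.1.2) records basal and bolus insulin during CGM monitoring. In 7.7.1 the sensor is mounted as the last step of the baseline visit, after the blood draw in the order described. The diary is therefore not stated to cover the dose before the draw. Adjustment for daily units would help but could not fully recover what was circulating at sampling.

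**3. Is a marker of endogenous secretion already collected?** Yes. C-peptide is not injected and is taken at the same visit (8.1.4, Table 1). Glucose is not named in the 8.1.4 list, but the arginine test includes a sample at -15 min, before the infusion at -1 min, analysed for both glucose and C-peptide (8.1.5). A basal C-peptide with concurrent glucose therefore exists under the current schedule. What is missing is a statement that C-peptide, rather than insulin, represents the beta cell in the profile related to CGM metrics.

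**4. Illustration of size.** Suppose endogenous secretion has no effect and that measured insulin and glucose variability are linked only through injected dose. Let r1 be the correlation of measured insulin with dose, and r2 that of dose with variability. Both are assumptions; the documents give neither. Then

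- induced correlation: r = r1 × r2
- m = atanh(r) × √(n − 3)
- P(two-sided p<0.05) ≈ 1 − Φ(1.96 − m) + Φ(−1.96 − m)

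Example with n = 30, r1 = 0.7, r2 = 0.5: r = 0.35, atanh(r) = 0.365, √27 = 5.196, m = 1.90, and P = 1 − Φ(0.06) ≈ 0.48.

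| r1 | r (r2 = 0.3 to 0.5) | P at n = 30 | P at n = 24 |
|---|---|---|---|
| 0 | 0 | 5% | 5% |
| 0.5 | 0.15 to 0.25 | 12% to 26% | 11% to 22% |
| 0.7 | 0.21 to 0.35 | 20% to 48% | 16% to 39% |
| 0.9 | 0.27 to 0.45 | 30% to 71% | 25% to 60% |

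The sample sizes are those of 7.8, with and without the dropout allowance. The row r1 = 0 corresponds to measured insulin that carries no trace of injected dose, for example with an assay that does not read the injected product. The table shows how the risk grows; it does not estimate it for this trial.

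**The case against.** The best defence is that secretion is already measured properly. C-peptide is taken at baseline and in the arginine test, and no section says that secretion will be derived from circulating insulin. Section 8.1.4 speaks of circulating levels, which is literally true of a mixed measurement. Section 7.6.3 does not single out insulin or commit to reading it as endogenous. Covariate adjustment is ordinary material for a statistical analysis plan, and regimen and daily units are recorded.

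Much of this stands. Unstated adjustment is not a fault of the protocol. The illustrative rates rest on assumed correlations. What does not fall away is the classification. Sections 7.7.1 and 8.1.4 put insulin among the pancreatic hormones, and 7.6.3 relates that group to CGM metrics as possible mediators. The analyte and its sampling conditions are fixed in the protocol, and a later analysis plan cannot recover a dose time that was not recorded.

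Two stronger readings are tempting and unsupported:

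- A reader might infer that the measured insulin simply shows the last injection. The documents support only a mix of unknown proportion, anywhere from mostly endogenous to mostly injected.
- A reader might infer that 7.6.3 and 8.1.5 contradict each other, because the former says "an arginine test is employed to study pancreatic endocrine secretory capacity (insulin and glucagon") while the latter assays C-peptide. They do not. One names what the gland secretes and the other the analyte, and C-peptide is a coherent measure of insulin secretion.

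**Conclusion.** The point holds for one exploratory analysis. As planned, an association between baseline insulin and CGM metrics cannot be separated from injected insulin, which is itself a cause of the outcome. It rests on three premises, the first two of which are in the protocol: every sampled patient is insulin treated, insulin is grouped with the pancreatic hormones examined as possible mediators, and injected insulin contributes to the measured value. The size of that contribution is unknown.

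It would be wrong to infer that the trial's main conclusions are affected. No primary or secondary endpoint (7.6.1, 7.6.2) and no sample size (7.8) depends on this measurement, and the arginine assessment does not use insulin as an analyte. A reversed sign is possible but not shown. C-peptide settles the source of the hormone; it does not remove every form of confounding by treatment, and how to handle the remainder can be left to the analysis plan.

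**What to change.** - **7.6.3 and 8.1.4:** name baseline C-peptide, with concurrent glucose, as the beta-cell marker in the hormone profile related to CGM metrics. The pre-infusion sample of the arginine test supplies both values.
- **If insulin is still assayed:** label it total circulating insulin, report it descriptively, and state that it is not interpreted as pancreatic secretion. Recording the assay and the type and time of the last dose before the draw would make the value easier to read.
- **Optional:** say in 7.6.3 that insulin secretion in the arginine test is measured by C-peptide. This is a clarification, not a correction.

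The cost is a wording change in two sections. No new blood sample is needed and no treatment changes. Recording the last dose, if adopted, is one small extra data item at the baseline visit. Dropping the insulin assay would save its cost.

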8.1.5 Arginine stimulation test

An intravenous catheter is inserted into the cubital vein for blood sampling and arginine infusion with arterialization of the venous blood using the heated hand technique. At time -1 min 5 g argininehydrochlorid (100 mg/mL) is infused over 1 minute. Blood samples are drawn at time -15, 0, 2, 5, 10, 15 and 30 min for the analysis of blood glucose, plasma C-peptide and glucagon. These blood samples will be kept on ice and immediately separated by centrifugation and processed as plasma and subsequently transferred in aliquots to vials labelled with the protocol number (PPDM-CGM_2022), subject number, and date of sample collection. Samples will be frozen and stored at approximately -80°C or cooler in a freezer at Aalborg University Hospital until analysis. The samples will be batch analysed at a central laboratory to measure the analytes of interest. After the analyses, spare blood will be kept in the biobank for future research purposes and destroyed at the latest 15 years after termination of the study. Ethics according to “databeskyttelsesforordningen” and “databeskyttelsesloven” will be ensured in this regard. In total, 56 ml blood will be drawn from each participant during the arginine stimulation test.

